- b) examine whether the reduction of drinking in phase 1 initial 12-week treatment responders (defined as ≥60% reduction in drinks/wk during weeks 9-12) can be maintained in a 12-week double blind phase 2 extension of the initial treatment condition to help identify the clinical utility of dutasteride as a treatment for AUD, which is a chronic relapsing disorder;
- **c)** examine whether pbo arm non-responders during phase 1 experience a reduction in drinking when crossed over to dutasteride during the 12-week phase 2 extension; and **d)** examine the moderating effects on treatment outcomes of baseline self-reports of drinking to cope, trait anxiety, perceived stress, adverse child experiences and a polymorphism (rs1360780) in the *FKBP5* gene encoding a key chaperone protein regulating functions of androgen, progesterone and glucocorticoid receptors that has been

associated with negative behavioral responses to life stressors, including increased heavy drinking in college students (Lieberman, Armeli et al. 2016) and a stronger linkage between drinking to cope and next day emotional depletion.

Specific Aims.

Aim 1. To examine the safety, tolerability and efficacy of dutasteride in helping patients with AUD to reduce or stop drinking, 190 treatment-seeking men and women with AUD who drink heavily on a regular basis (\geq 24 standard drinks / week for men and \geq 18 drinks/week for women) will be randomly assigned to treatment with either dutasteride or pbo for 12 weeks. A biological marker (PEth phosphatidylethanol) will be used as a secondary measure of change in alcohol use and the dihydrotestosterone (DHT) metabolite 3α -androstanediol glucuronide will be used to monitor dutasteride inhibition of 5α -reductase enzyme activity. We hypothesize that dutasteride 1 mg/day will be well tolerated by both male and female heavy drinkers, will produce \geq 80% reduction in the serum marker of 5α -reductase enzyme activity and will result in a greater reduction in the number of heavy drinking days and drinks per week than pbo and that treatment effects will be greater for women as they are expected to more frequently experience drinking to cope, higher anxiety and a history of childhood adversity/trauma.

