comparison in phase 1 and a within-subjects test in phase 2 for patients treated with pbo in phase 1 and dutasteride in phase 2, iii) allow evaluation of whether reductions in drinking are maintained with ongoing treatment for phase 1 dutasteride responders, and iv) provide preliminary data on whether dutasteride non-responders show reductions in drinking when crossed over to naltrexone, an established medication for AUD with a different mechanism of action compared with dutasteride.

Three and six-month follow-up visits following the completion of the 24-week treatment phase will evaluate the durability of treatment effects, allow measurement of the degree to which dutasteride effects on 5AR inhibition have been reversed following 12- or 24-week exposures and to maintain contact with female participants to remind them of the importance of effective contraception for 6 months following treatment.

Table 1. Expected Patient Distribution for Phase 1 and 2.

Phase 1	Phase 1	Phase 1	Phase 2	Phase 2 Statistical contrasts
Treatment	Statistical	Expected Tx	Treatment	
	contrasts	response groups		
Dutasteride n=95 (grp A)	Between-subject contrasts using GLMM Dut vs. Pbo for DVs HDD/wk and SD/wk;.	Dut-R (wk 9-12 Response n=40) Dut-NR (wk 9- 12 Non-Response n=40)	Dut-R dutasteride Dut-NR naltrexone	Within-subject interrupted time series regression using mixed models. Dut-R: Is dut response maintained? Dut-NR: Do dut NRs respond to naltrexone?
	Moderating			
Pbo n=95 (grp B)	effects of genotype, baseline state vs. trait anxiety, perceived stress and interaction with FKBP5 genotype	Pbo-R (wk 9-12 Response n=16) Pbo-NR (wk 9- 12 Non-Response n=64)	Pbo-R pbo Pbo-NR dutasteride	Pbo-R: insufficient sample for statistical comparison. Pbo-NR: Do pbo NRs respond to Dut?

Phase 1 response ≥ 60% reduction SD/wk for wk 9-12 vs baseline (current study 49% response rate for dut vs. 20% pbo). dutasteride 1 mg/day; naltrexone 50 mg/day.

2.C.2. Patients: Drinkers who want to reduce or stop drinking will be recruited using advertisements in radio and print media, by posting/distributing recruitment materials in community settings, informational mailings to area clinicians and by referral from UConn Health medical and dental clinics in at our main campus in Farmington CT together with

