satellite outpatient clinics in Canton, East Hartford, Putnam, Simsbury, Southington, Storrs, and West Hartford CT. Based on prior UConn ARC pharmacotherapy trials open to men and women (Kranzler, Tennen et al. 2009, Kranzler, Armeli et al. 2011, Kranzler, [name] et al. 2014) we anticipate that 35% of subjects will be female. Approximately 260 subjects will be enrolled (in person screening visit) with the goal of randomizing 190 to medication with 160 completing the initial 12 weeks of treatment. In the current study limited to men only, we enrolled 189 men and of these randomized 142. At least four factors will contribute to success in enhancing our recruitment in order to randomize 190 subjects in the proposed study: i) inclusion of women (35% of subjects), ii) UCONN Health has recently adopted the EPIC electronic medical record system which includes clinical trial notice pop up feature on clinicians' patient management screens with link to information about our clinical trial for patients with a clinic problem list entry of alcohol use disorder, iii) involvement of [name] as a co-investigator who is the past-president and current board member of the CT Chapter of the American Society for Addiction Medicine and has agreed to send an informational letter and recruitment flyers for the study to all central CT members of ASAM, and iv) the PI's greater experience in recruitment compared with the current study which was the first clinical trial for which he served as Principal Investigator.

2.C.2.a. Temporal Sequence of Screening: Prospective participants will first undergo phone screening including the AUDIT-C three-item screener (Dawson, Grant et al. 2005) to assess key inclusion / exclusion criteria. Patients who appear to be eligible will be invited for an in-person screening. After informed consent is obtained, staff will administer several questionnaires, obtain a medical history, collect urine and blood specimens for clinical screening and for genotyping the *FKBP5* rs1360780 polymorphism to allow balanced genotype distributions in the dutasteride and pbo treatment arms. Patients will receive a physical examination by a study physician and if no exclusions are identified will be randomized to receive study medication.

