- 2.C.3.d. Medication Randomization and Drug Accountability: Urn randomization (Stout, Wirtz et al. 1994) will be used to assign subjects 1:1 to dutasteride or pbo for treatment phase 1, balancing for number of DSM5 AUD criteria (2-5 vs.>5), DTC relative to total motives score (0-25% vs. >25%), *FKBP5* genotype (CC vs. T-carrier), current smoking status, and use of medication for treatment of co-morbid psychiatric condition. Separate

randomizations will be done for women and men to ensure balance on these variables in both sex groups. At the end of phase 1, patients who have reduced drinks/week by at least 60% will continue for the second 12 wks on the originally randomized treatment taking 2 capsules per day. Subjects who have reduced drinks/wk by less than 60%, will be informed that they will be transitioning to an active study medication (either dutasteride or naltrexone), and will be interviewed to confirm they have not used opioid medication for 5 days prior which will be verified by urine testing, subjects testing positive for opioids will not be eligible for starting phase 2. For non-responder subjects in the phase 1 pbo arm, the pharmacy will begin dispensing 0.5 mg dutasteride capsules with instructions to take 1 capsule per day for 2 days, then 2 capsules daily for 12 weeks. For subjects in the initial dutasteride arm and reducing less than 60%, the pharmacy will dispense 25 mg naltrexone capsules with the same instructions of 1 capsule for days 1 and 2 followed by 2 capsules each day (50 mg naltrexone per day) to match the dutasteride capsule dosing. Medication vials including any unused medication will brought to each follow-up visit. Unused pill counts will be recorded by the study nurse at each bi-weekly visit and medication use recorded daily by patients on their drink log.

2.C.4. Study Visits:

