2.C.8 Exploratory microbiome analysis Leclercq et al (Leclercq, Matamoros et al. 2014, Leclercq, de Timary et al. 2017) have reported that as many as 40% of alcohol dependent subjects may harbor pro-inflammatory gut microbiota contributing to increased gut permeability which was associated with higher anxiety and alcohol craving after 3 weeks of abstinence. Our hypothesis is that participants with higher levels of pro-inflammatory gut microbes at baseline will have less success in reducing drinking. Stool samples will be collected by participants at home and transported to the CRC in a small cooler with freezer packs. Samples will be stored at -80C until batch processed. DNA will be prepared from stool samples and used for metagenomics whole genome shotgun sequencing of microbial DNA. This method allows species and strain level identification of the gut microbiome. Analysis of sequence data and comparison of strains by treatment response will be done by [name] Assistant Professor of Medicine at UConn Health who is an experienced investigator in molecular characterization of human microbiomes. Correlations of the relative abundance of microbes in baseline stool samples with participant success and in reducing weekly drinking will be examined. We will also examine change in microbiome between baseline and endpoint as a function of change in drinking.

2.C.9. Data Analysis:

2.C.9.a.1. Safety: Safety will be analyzed using categorical outcomes, defined by the type and severity of adverse effects. Summary measures of adverse effects (AEs) will be developed by organ system from the SAFTEE adverse event checklist and will be compared for patients receiving dutasteride or pbo using χ^2 analysis in phase 1 and

comparing patients switched to dutasteride vs. naltrexone in phase 2. Comparisons will be conducted on 1) the proportion of patients in each of the comparison groups who report AEs, 2) the proportion of patients in each of the comparison groups who report moderate-to-severe AEs, and 3) the proportion of patients in each comparison group who discontinue treatment due to AEs. Individual AEs that occur in \geq 5% of patients in either medication condition will be examined using χ^2 analysis.

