For the phase 1 comparison of dutasteride and pbo over time, efficacy analyses will be performed using generalized linear mixed (GLMM) models implemented in SPSS. GLMM incorporates within subject correlation effects important in examination of repeated measures, can incorporate multiple covariates, interactions, random and fixed effects, nonnormal distributions, and is often recommended for designs such as proposed (Mallinckrodt C 2017). Medication group will be treated as a factor and treatment week as a continuous covariate. Sex, smoking status, treatment goal (stop vs. reduce drinking), and use of concurrent medication for co-morbid psychiatric conditions will also be examined as baseline between-subject covariates. Medication group, week, and the other covariates will be modeled as fixed effects, and the intercept will be modeled as random effects. For the outcome HDD/wk a binomial distribution with logit link will be used where the number of HDD during the week will be the numerator and number of observed days the denominator. For the outcome SD/wk a negative binomial distribution with log link will be used. An interaction term between medication group and the week term(s) will be used to evaluate whether the efficacy of dutasteride compared to pbo in reducing drinking varies over time. Interaction effects of sex and treatment condition will also be examined. Pretreatment drinking will be controlled using baseline TLFB drinking data as a covariate. The robustness of results will be evaluated by running the model under three different conditions: 1) modified intention to treat using all available outcome information from subjects with at least 1 post-randomization visit, 2) data from 12-week per protocol completers, and 3) multiple imputation using 10 imputed data sets with weekly drinking and baseline covariates thought predictive of the outcomes or missingness included in the imputation phase.

For aim 2, phase 2 outcomes, the within-subjects analysis will compare drinking during phase 1 against phase 2 for three groups: a) patients responsive to dutasteride in phase 1 and continuing on dutasteride for an additional 12-weeks in phase 2, to examine whether the response is maintained with continued treatment; b) phase 1 non-responders crossed over from pbo in phase 1 to dutasteride in phase 2 to provide a second contrast using an A-B design of the efficacy of dutasteride compared with pbo; and c) phase 1

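### No adverse event comparison is planned by sex, and the arm-wide 5% screen leaves a women-only event seen in up to 4 of about 33 women untested individually, although Aim 1 hypothesises tolerability in women

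*Combined protocol and SAP*

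**What the plan says.** **The safety analysis.** Section 2.C.9.a.1 (Safety) sets out AE comparisons between dutasteride and placebo in phase 1, and between patients switched to dutasteride and to naltrexone in phase 2. "Summary measures of adverse effects (AEs) will be developed by organ system from the SAFTEE adverse event checklist", and these are compared between groups. Three proportions are also compared: patients with any AE, with moderate-to-severe AEs, and who discontinue because of AEs. Last comes a screen: individual AEs occurring in at least "5% of patients in either medication condition will be examined using" a chi-square test. The section does not mention sex.

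**What the trial wants to conclude.** Aim 1 hypothesises that dutasteride "will be well tolerated by both male and female heavy drinkers". Section 2.B.2 (Preliminary studies) reports a prior trial in men only.

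**What the design provides.**
- Section 2.C.2: "we anticipate that 35% of subjects will be female".
- Section 2.C.3.d: separate "randomizations will be done for women and men to ensure balance on these variables in both sex groups".
- Section 2.C.9.a.2 (Efficacy): sex is a covariate in the drinking model, and "Interaction effects of sex and treatment condition will also be examined". This applies to the drinking outcomes only.
- Section 2.C.6.b.4: side effects are collected on SAFTEE at each biweekly visit. Time since last menses is recorded for women, partly for safety monitoring, but no AE comparison among women is attached to it.

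**The concern.** The trial sets out to extend dutasteride for alcohol use disorder to women, and it states a tolerability hypothesis about them. The planned AE analysis contains nothing that estimates tolerability in women.

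Two features combine. First, every comparison is by arm with no sex split, so about 33 women are averaged with about 62 men. Second, the screen for individual AEs is a percentage of the whole arm. Women are about a third of it, so an event that occurs only in women must reach nearly three times the nominal rate among them (0.05/0.35 = 14.3%) before it is tested. At stake is whether the final report can support, qualify or refute the female half of the Aim 1 tolerability statement from a planned table.

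**Working it through.** The plan states no rate, power or sample size for the AE screen, so there is no figure of its own to reproduce. The size of the gap follows from stated inputs.

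**Inputs**
- Arm size: "Dutasteride n=95 (grp A)" in Table 1; placebo is also 95.
- Share of women: 35% (2.C.2).
- Screen: at least 5% in either arm (2.C.9.a.1).
- Alternative denominator: 2.C.2 expects 190 randomised "with 160 completing the initial 12 weeks of treatment", which is 80 per arm.

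**Step 1. Women per arm.** 0.35 × 95 = 33.25, about 33 women and 62 men.

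**Step 2. Cases needed.** 0.05 × 95 = 4.75, so 5 patients. Four cases fall below the screen: 4/95 = 4.2%.

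**Step 3. Largest untested observed rate in women.** With no affected man in the arm and placebo also below 5%, it is 4/33 = 12.1%. The first count that is tested is 5/33 = 15.2%.

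**Step 4. Sensitivity of that ceiling**

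| Setting | Largest untested count in women | Rate in women |
|---|---|---|
| Arm 95, 33 women, 0 men affected | 4 | 12.1% |
| 1 man affected | 3 | 9.1% |
| 2 men affected | 2 | 6.1% |
| 3 men affected | 1 | 3.0% |
| Arm 95, share of women assumed 30% (28 women), 0 men affected | 4 | 14.3% |
| Arm 95, share of women assumed 40% (38 women), 0 men affected | 4 | 10.5% |
| Completers, 80 per arm, 28 women, 0 men affected | 3 | 10.7% |
| Phase 2 placebo non-responders on dutasteride, 64, about 22 women, 0 men affected | 3 | 13.6% |

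The 30% and 40% shares are assumptions; the plan gives only 35%.

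**Step 5. How often the screen is reached.** The 12.1% is an observed proportion. For an assumed true rate p in women, with no cases in men or on placebo, the arm-wide screen is reached with probability P(X ≥ 5), where X is binomial(33, p). A 5% screen within women needs 0.05 × 33 = 1.65, so 2 cases.

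| True rate in women | Arm-wide screen reached | Within-women screen reached |
|---|---|---|
| 8% | 12% | 75% |
| 10% | 23% | 86% |
| 12% | 36% | 92% |

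These are chances that a test is run, not that a difference is found. At a 10% rate in women, a background rate in 62 men assumed at 1%, 2%, 3% or 5% raises the arm-wide figure from 23% to 35%, 48%, 59% or 78%.

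**Step 6. What a within-women comparison could show.** For 4/33 versus 0/33, Fisher's exact p = 0.11, the uncorrected chi-square p = 0.039, and the continuity-corrected p = 0.12. For 2/33 versus 0/33, Fisher p = 0.49. Fisher power at the two-sided 5% level with 33 women per arm is about 11% for 10% versus 0% and 20% for 12% versus 0%.

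The estimate is still informative. The Wilson 95% limits are 4.8% to 27.3% for 4/33 and 0% to 10.4% for 0/33. The Newcombe interval for the difference of 12.1 points runs from 12.1 − √(7.3² + 10.4²) = −0.6 to 12.1 + (27.3 − 12.1) = 27.3 points.

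**The case against.** **Such an event is not ignored.** A reader might infer that it is never examined, or that the trial could call dutasteride well tolerated in women without having looked. The documents do not support that. The 5% screen governs only individual AEs. The organ-system and any-AE comparisons in 2.C.9.a.1 have no such filter and would include the event, as would the moderate-to-severe and discontinuation comparisons if it qualified. Under section 3.C the investigator evaluates every moderate or severe AE, and the safety board receives aggregate AE data twice a year. This stands, and it limits the point to individual testing. It does not remove the point: none of the comparisons in 2.C.9.a.1 is split by sex, and monitoring during the trial is not the end-of-trial evidence that Aim 1 needs.

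**The AEs named for women are not confined to women.** Section 3.A.3 lists headache, gastrointestinal discomfort and decreased libido. In the prior trial in men (2.B.2), stomach discomfort reached 16.4% and reduced libido 9.0% on dutasteride. If those rates recurred in 62 men with 10% of women affected, the arm-wide screen would be reached in 99.9% and 95% of trials. This stands too. Such events would be tested, though a larger effect in women would be averaged with the men.

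**Running a test is not detecting harm.** A reader might take 86% against 23% as a gain in detection. It is not, as the 11% power shows. The within-women screen would also flag noise: an AE with a true rate of 5% in both arms reaches 2 of 33 in one given arm with probability 0.496, so in at least one arm with probability 1 − 0.504² = 75%. This is why the tables should be descriptive.

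**The plan never promised AE tests by sex.** True, so this is an omission measured against the stated aim and not a contradiction in the text.

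**Conclusion.** The point holds as an inexpensive improvement to the safety analysis. The plan states a tolerability hypothesis for women and randomises them separately, but it plans no AE comparison by sex. Its screen would leave a women-only event in up to 4 of about 33 women on dutasteride (about 12%) untested as an individual AE.

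The 12% rests on 95 per arm, 35% women, no affected men in the arm, and a placebo rate below 5%. It is a ceiling on the observed proportion, not a true rate: at a true 12%, the event would still reach individual testing in about 36% of trials. That sexes are pooled is read from the absence of any split; the text does not say so outright. The absence of AE results by sex does not depend on the 12%.

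**What to change.** In 2.C.9.a.1:

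1. Apply the 5% threshold within each sex as well as overall, so that an AE is reported if it occurs in at least 5% of all patients, of women, or of men in either arm.
2. Tabulate phase 1 AEs, moderate-to-severe AEs and discontinuations due to AEs by arm within sex.
3. Give risk differences with confidence intervals, or exact tests where counts are small, in place of relying on chi-square alone.
4. Label the within-sex results descriptive, and base any statement on tolerability in women on these tables, with their intervals.

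The cost is wording and extra tables. Sex and SAFTEE reports are already recorded, so no new data are needed. The drawback is more comparisons, some of which will be chance findings, with low power in about 33 women per arm.

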At the end of phase 1 treatment week 12 (visit 8) and phase 2 treatment week 24 (visit 14), subjects will complete a series of questionnaires and be interviewed by research staff concerning their alcohol consumption and alcohol-related symptomatology. For subjects who withdraw early and do not wish to continue with study visits/procedures, end-of-treatment evaluations will be administered at the time of withdrawal. Such subjects will also be invited to participate in-person or by telephone to provide drinking data for the 12-, 24-week time points in order to include this data in intent to treat analysis of the treatment phase.

2.C.4.d. Visits 15 and 16 (3- and 6-month Post-treatment Assessment): To evaluate the durability of treatment effects, patients will be invited to return to the clinic for a post-treatment assessment 3 and 6 months after completion of treatment (if unable to come in person a telephone interview will be conducted). Subjects will be contacted 6-8 weeks after end of treatment and following the 3-month follow-up visit to remind them of their follow-up appointment dates, reinforce maintaining their written drinking diary and to remind female subjects of the importance of continued use of effective contraception for 6 months following treatment. At each follow-up visit, subjects will complete self-report questionnaires and will be interviewed by the research staff. Blood samples for measurement of serum PEth, and 3α -diolG will be obtained. Subjects will be paid \$50 for participating in each post treatment visit.

2.C.5. Medical Management: A study physician will meet with each subject at the beginning of treatment. The PI will consult at least weekly with study staff to monitor potential study-related side effects and will be available to personally evaluate subjects with severe or persistent adverse effects. At each treatment encounter, subjects will receive brief counseling as part of medical management, described below.

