2.C.6.a. Laboratory/Medical Assessments: A physical examination, urinalysis, urine toxicology, serum bHCG (for women), CBC, and a chemistry panel (which includes electrolytes, liver enzymes [ASAT, ALAT, GGT], direct bilirubin, BUN, and creatinine) will be used to screen subjects for medical exclusion criteria. ASAT, ALAT will be repeated for subjects with elevations at baseline greater than 3x normal at weeks 6, 12, 18 and 24 (or until reduced to less than 3x normal). Weight, blood pressure and pulse will be obtained at each treatment visit. Urine will be tested every 6 weeks for drugs of abuse and HCG for women of reproductive potential. Blood will be archived for measurement of phosphatidylethanol (PEth) by a commercial testing lab as an objective measure of alcohol use. PEth is an alcohol-specific adduct catalyzed by phospholipase D from ethanol and phosphatidylcholine in membranes of red blood cells and is not affected by liver or kidney disease, age or sex. It is a sensitive and specific metabolite which is produced in direct response to use of alcohol during the past 20-30 days (Viel, Boscolo-Berto et al. 2012). PEth levels are correlated with the amount of alcohol consumed (Aradottir, Asanovska et al. 2006) and correlate better with daily diary drinking reports than carbohydrate deficient transferrin or gamma glutamyl transferase (de Bejczy, Lof et al. 2015, Walther, de Bejczy et al. 2015). Blood for PEth will be collected at screening, and weeks 6, 12, 18 and 24. Serum 3α-diolG will be measured using a commercial ELISA kit as a biochemical measure of 5AR inhibition by dutasteride. 3α -diolG is a major metabolite of testosterone and is more abundant that DHT especially in women and has been shown to decrease in parallel

with DHT following finasteride treatment in men (Rittmaster, Stoner et al. 1989, Gormley, Stoner et al. 1990) and has been used to monitor the reduction of 5AR activity in women treated with finasteride (Wong, Morris et al. 1995, Falsetti, Gambera et al. 1999). Serum testosterone, estradiol, progesterone, cortisol, ACTH and sex hormone binding globulin will be measured using commercial immunoassays to evaluate changes in these steroid hormones during treatment with dutasteride. Blood for 3α -diolG and steroid hormones will be collected at screening and weeks 6, 12, 18 and 24.

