Study Visit	V1 Screen	V2 Baseline	V 3-7	phase 2 baseline	V 9-13	V14	V15-16
Time relative to Medication		Start medication	wks 2, 4,6,8,10	wk 12 end phase 1	wks 14, 16,18,20,22	wk 24 end phase 2	3- and 6- mo follow- up
Medical History, demographics, AUDIT, SCID, FHAM, ACES, TESI, STAI-trait, Clinical screening labs, blood for DNA and research analytes Physical Exam & Clinician review of Medical History	x						

TLFB, PHQ-9, CIWA, MTR	X	Х	X	X	Χ	X	Χ
Vital signs & weight	Х	Х	X	Х	Х	Х	Х
DMQ, AEQ, SIP	Х			Х		Х	Х
Study outcome blood samples	Х		wk 6	Х	wk 18	Х	Χ
Urine drug screen, HCG (women), PACS	Х		wk 6	Х	wk 18	Х	Х
STAI-state, PSS		Х					
STAI-trait, PSS				Х		Х	Х
Daily IVR call		Х	wk 1-4	wk 9-12		wk 21-24	
Side Effect Checklist (SAFTEE)		Х	Х	Х	Х	Х	Х
Medical Management		Х	Х	Х	Х	Х	
Alcohol SCID past 1 month				Х		Х	Х

The IVR system will use the same procedures we have used in the recently completed dutasteride study and prior UConn Health studies of topiramate (Kranzler, Armeli et al. 2016). a) Daily drinking diary: Every evening, as part of the IVR daily diary, patients will record their alcohol consumption as the number of standard drinks in each of three categories of alcoholic beverages: beer, wine, liquor. Patients are asked to report separately drinking from yesterday and any drinking during the current day, up until the time of the IVR report. This allows us to examine lagged associations with mood and life event triggers. b) Daily mood: Patients will be asked to rate as part of the daily IVR their mood using an adjective checklist. The checklist consists of 9 adjectives (Larsen and Diener 1992) with each rated on a 5-point scale (0 = "not at all" to 4 = "extremely"). Three adjectives for each of three mood state dimensions provide measures of positive mood, negative mood and activated mood. Subjects will also be asked to report their self-efficacy for managing life problems. c) Daily Events: Participants will be asked whether they experienced a list of nine possible daily events (3 stressful, 3 pleasant, and 3 situations where someone might drink). These measures will be used to assess the influence of positive and negative current life events on drinking. d) Drinking motives: Participants will be asked to respond to 3-items for each of three drinking motives as to why they drank today and yesterday; to cope, to enhance or to socialize on a 3-point scale (1= "not at all", 2="somewhat" and 3="definitely).

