2.C.9.a.2. Efficacy: Primary treatment outcomes will be defined in terms of HDD/wk and SD/wk based on TLFB reports of drinking. Reduction in these measures is related to health benefits of reduced drinking. These are the measures that are used to define non-hazardous drinking. Secondary outcomes will include proportion of days abstinent (PDA), % of subjects with no HDDs, % of subjects with non-hazardous drinking (no HDD and SD/week <15 men/<8 women) during the last 4 weeks of each treatment phase, and change in PEth at end of each treatment phase relative to baseline.

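### PEth, the only objective drinking outcome, has no stated adjustment for its own baseline, and its phase 2 change is set against an unqualified baseline that does not fit the phase 2 question

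*Combined protocol and SAP*

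**What the plan says.** Aim 1 states that PEth "will be used as a secondary measure of change in alcohol use", and section 2.C.6.a describes it "as an objective measure of alcohol use". Section 2.C.9.a.2 bases the primary outcomes on Timeline Follow-Back reports. The remaining secondary outcomes are also counts of drinks or drinking days. PEth enters that list as "change in PEth at end of each treatment phase relative to baseline".

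The same section describes generalized linear mixed models for the phase 1 efficacy analyses and gives distributions for heavy drinking days and drinks per week only. On baseline it says: "Pretreatment drinking will be controlled using baseline TLFB drinking data as a covariate". No scale, model or covariate is given for PEth.

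Section 2.C.6.a sets the sampling times: "Blood for PEth will be collected at screening, and weeks 6, 12, 18 and 24". Table 2 (Schedule of Assessments) shows no outcome blood sample at visit 2, so screening is the only pre-treatment value. The same table labels the week 12 visit "phase 2 baseline".

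For phase 2, section 2.C.9.a.2 plans within-patient comparisons of phase 2 drinking with phase 1 drinking in three groups, plus a restricted comparison of the final four weeks of each phase. For the dutasteride responders it sets a non-inferiority margin of 20% over phase 1 levels. PEth is not mentioned there.

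Section 2.C.4.d lists, for the 3- and 6-month follow-up visits, "Blood samples for measurement of serum PEth". Section 2.C.6.a locates PEth in red-cell membranes.

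**The concern.** PEth is the check on self-report in a trial whose primary outcomes are both self-reported, so it should be analysed efficiently and should answer the same question as the outcome it supports.

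In phase 1, the endpoint is a change score and the only pretreatment covariate named is self-reported drinking. An analyst following the text literally could compare mean changes without using screening PEth as a covariate, and lose power for no gain.

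In phase 2, one unqualified baseline serves both phases. Read naturally as screening, it gives a week 24 change that combines what happened in both phases, whereas the phase 2 question is what happened after week 12. Switchers could appear to benefit from the second drug because of a fall that preceded it. Responders could appear to have held their gain when part of it has gone.

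**Working it through.** The documents give no power, standard deviation or correlation for PEth, so there is no planned figure to reproduce. Every correlation, shift and spread below is an assumption.

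**Phase 1 precision.** Let s² be the PEth variance (same at screening and follow-up) and r their correlation.

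- Change score: variance 2(1 − r)s².
- Adjusted for screening PEth: variance (1 − r²)s² = (1 − r)(1 + r)s².
- Ratio, adjusted to change: (1 + r)/2. The change score needs 2/(1 + r) times as many patients.

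The power columns use 80 per arm (section 2.C.9.b), two-sided 5%, and a true difference of 0.4 follow-up SD. The 0.4 is borrowed from the drinking power statement for illustration.

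| Assumed r | Ratio | Extra patients, unadjusted | Power, change score | Power, adjusted |
|---|---|---|---|---|
| 0.3 | 0.65 | 54% | 57% | 76% |
| 0.5 | 0.75 | 33% | 72% | 83% |
| 0.7 | 0.85 | 18% | 90% | 94% |
| 0.8 | 0.90 | 11% | 98% | 99% |

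With screening PEth as a covariate, modelling the change or the final value gives the same treatment estimate, so the loss is zero.

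**Phase 2, switchers.** By identity:

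(week 24 − screening) = (week 12 − screening) + (week 24 − week 12).

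Only the last term belongs to the second drug. A placebo non-responder whose PEth fell 25% in phase 1 and stayed level in phase 2 scores −25% at week 24. Such falls are compatible with non-response, which section 2.C.3.d defines as less than a 60% reduction in drinks per week.

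Table 1 expects 64 placebo and 40 dutasteride non-responders, so 104 of 160 switch (65%). Take the 64, a second drug with no effect, and a phase 1 fall of c SD. The standardised paired change from screening is c/√(2(1 − r)). The chance that a two-sided 5% paired t-test is significant is:

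| Phase 1 fall c | r = 0.5 | r = 0.7 |
|---|---|---|
| 0.2 SD | 35% | 53% |
| 0.3 SD | 66% | 86% |
| 0.4 SD | 88% | 98% |

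**Phase 2, dutasteride responders (40 expected).** Take PEth of 100 at screening, 40 at week 12 and 70 at week 24. Against week 12 this is 70/40 − 1 = +75%. Against screening it is 70/100 − 1 = −30%. The first shows response being lost; the second reads as continuing benefit.

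**Is week 12 a clean reference?** Not for switchers, who are selected on weeks 9–12 drinking. An illustrative log-normal simulation used log SD 0.7, correlations of 0.5 and 0.7, phase 1 mean shifts from 0 to −0.6, a null second drug, and PEth itself as the selection variable. Week 24 minus week 12 still fell by 0.05 to 0.29 SD of the paired change. At shifts of −0.4 and −0.6, the screening reference fell by 0.40 to 0.93 and the week 12 reference by 0.16 to 0.29. With no phase 1 shift the two biases were similar in size (0.05 to 0.10) and opposite in sign. The advantage of week 12 therefore grows with the phase 1 fall.

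**The case against.** The strongest reply is that section 2.C.9.a.2 defines an endpoint and does not prescribe its analysis. A reader might infer that the plan commits to a raw, unadjusted change analysis. It does not: neither term appears, the section describes covariate-adjusted mixed models for phase 1 efficacy, and baseline PEth is unstated rather than excluded. The precision loss is therefore conditional, and it is small at high correlations. The reply does not remove the gap, because the only pretreatment covariate named is Timeline Follow-Back drinking.

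A reader might also infer that PEth is unable to support the phase 2 comparisons. That goes too far. The outcome is specified at the end of each phase, and the two changes differ by exactly week 24 minus week 12, so the needed quantity is collected and recoverable. The week 12 column label in Table 2 also leaves room to read baseline as week 12 for phase 2, and nothing says that week 24 minus screening will test the second drug. What stands is that the reference is undefined and that its natural reading does not match the stated phase 2 question.

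It is fair to add that change from screening is a sensible overall description for responders, who stay on their first treatment. It does not answer whether the week 12 response was kept.

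Section 2.C.4.c says that, for early withdrawals, "end-of-treatment evaluations will be administered at the time of withdrawal". A reader might infer that an early PEth value would stand in for the phase-end value and reflect mainly pre-treatment drinking. The documents do not support this. That section describes questionnaires and an interview and mentions no PEth draw at withdrawal. With the 20–30 day window in section 2.C.6.a, even a sample at day 21 would cover 70% (21/30) to 100% on-treatment time.

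The serum wording concerns the follow-up visits, which lie outside the PEth endpoint, and has no bearing on the two main points.

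**Conclusion.** The concern holds as a gap in specification with a definite consequence under the natural reading. Baseline PEth is not named as a covariate. If it is left out, the phase 1 comparison needs 54% to 11% more patients across assumed correlations of 0.3 to 0.8, given equal variances; if it is included, nothing is lost. Week 24 minus screening does not match the phase 2 versus phase 1 question. In switchers it includes the phase 1 change, and with an inert second drug and assumed falls of 0.2 to 0.4 SD it would be significant 35% to 88% of the time at r = 0.5. In dutasteride responders it can hide loss of response. The primary analyses are unaffected.

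**What to change.** In section 2.C.9.a.2, add a short PEth paragraph:

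- **Phase 1.** Compare arms on log PEth at weeks 6 and 12 in a repeated-measures model with log screening PEth as a covariate. Place each sample at its actual week, and state a rule for values below the limit of detection.
- **Phase 2.** Reference weeks 18 and 24 to week 12, in line with the drinking analysis. Change from screening may be kept as a description.
- **Caveat.** State that regression to the mean remains in switchers because they are selected on weeks 9–12 drinking. The plan's own comparison of the final four weeks of each phase shares this limitation.

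Separately, reconcile the specimen named for PEth at visits 15 and 16 (section 2.C.4.d) with section 2.C.6.a.

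The cost is analysis wording and one specimen clarification. The samples at screening and weeks 6, 12, 18 and 24 are already planned, so no visit or blood draw is added.
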